4 STUDY DESIGN

4.1 OVERALL DESIGN

This phase 2 cluster-randomized parallel groups trial will test the efficacy of the MASLIHAT intervention model on reducing risky drug, alcohol, and sexual behaviors among male Tajik labor migrants who inject drugs while working in Moscow in comparison with a control condition. This study will be conducted at the Moscow satellite site of PRIZMA Research and Training Center directed by [name]. We include only men because few Tajik labor migrants are women, and moreover injection drug use among Tajik women is rare. However, the intervention presumably will benefit the female sex partners of participants when the men return to Tajikistan. Recruitment will be conducted by outreach at twelve distinct sites, including diaspora organizations, bazaars, and worksites.

We will use cluster randomization, with each recruitment site being randomized to one arm of the study. The Tajik Diaspora Union, under the leadership of [name] (consultant), will assist with referrals. In both study arms, the recruited men (index participants) will be required to recruit two eligible MWID peers for interviews prior to being interviewed themselves. After peer-recruited network members are enrolled and interviewed, the index participant will participate in the MASLIHAT training as peer educators or the control group activities depending on their recruitment site. All participants

and network members will then be followed and re-interviewed at 3-month intervals for one year to assess changes in risky drug, alcohol, and sexual behaviors due to intervention participation and through diffusion to network members. We will also collect data from voluntary HIV and HCV testing conducted at 6 months (HCV) and at 12 months (HIV and HCV) post-intervention.

In the MASLIHAT intervention, we will train Tajik migrant MWID as peer educators who will deliver the intervention to their network members both during the five-week training and after completion. We will assess changes in drug, alcohol, and sexual risk behavior at 3, 6, 9 and 12 months post-intervention. **We hypothesize that the MASLIHAT intervention participants and their network members will experience a greater reduction in risk behavior compared to those in the control condition.**

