9.2 SAMPLE SIZE DETERMINATION

We estimated power allowing up to 10% attrition among intervention participants and up to 15% attrition among network members. Power calculations were computed using PASS software and considering effects observed in the pilot study.

We expect to see large reductions in syringe sharing and condomless sex in the MASLIHAT intervention group, and little change in these behaviors in the control group. In the pilot study, syringe sharing decreased from 52% at baseline to 0% at six months, and condomless sex decreased from 35% at baseline to 1% at six months. For binary outcomes, we computed Mixed Models Tests for Two Proportions in a 3-Level Hierarchical Design (Level-3 Randomization), with an intracluster correlation of 0.05 and alpha=.01. We computed power for outcomes ranging from 0.30 to 0.50 for the control group, and 0.05 to 0.15 for the MASLIHAT intervention group, and with 10, 20 or 30 subjects per cluster, representing intervention participants, network members, and the complete sample. We will have at least 80% power to detect predicted changes in condomless sex, and over 90% power to detect predicted changes in syringe sharing. In the larger sample, we will have adequate power to detect effects even if they are not as large as anticipated.

The intervention also targets alcohol use and in the pilot study, days of alcohol use in the past month decreased from 5 to 2, with $b/SE = -6.52$, yielding a Cohen's d effect size of -0.69. We estimated power by computing Mixed Models Tests for the Slope Difference in a 3-Level Hierarchical Design with Fixed Slopes (Level-3 Randomization), with subject $icc=0.30$ and $alpha=0.01$, for a standardized mean difference (SMD) of 0.50 to 0.70, with cluster sizes of 10, 20. and 30. For the intervention participants, we will have at least 80% power to detect a $SMD=0.70$; for network members we will have at least 80% power to detect a $SMD=0.50$, and for the complete sample we will have at least 80% power to detect a $SMD=0.41$.

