9.4 STATISTICAL ANALYSES

9.4.1 GENERAL APPROACH

Descriptive analyses of the study sample will include percentages for categorical variables and means and standard deviations for continuous measures. Chi-square tests and t-tests will be computed to compare study arms on baseline sociodemographic measures. We will compare follow-up between conditions using GEE logistic regression. Results will be reported as odds ratios with 95% confidence intervals and exact p-values for 2-tailed tests.

We will examine the distributions of outcome measures to ascertain whether there is sufficient variability to analyze frequency measures as ordinal. Response categories with a small number of responses will be collapsed for analysis. We will analyze missing data patterns to assess the extent of missing data, and to determine if there is evidence of non-ignorable missingness (i.e. missing not at random, MNAR).

We will conduct repeated measures linear, logistic, and modified Poisson regressions using mixed effects models with random intercepts for subject and recruitment site to test the effect of intervention condition on changes in mediator and outcome variables. In the event of missing data in more than 5% of cases, or unbalanced loss-to-follow-up, analyses will be conducted in Mplus using full-information maximum likelihood methods. We will include the interaction of time and participant type (intervention participant vs. network member) to test for differential effects. Following analysis of the main outcomes we will conduct analyses to explore hypothesized mediation and moderation effects.

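### The alcohol power in Section 9.2 leaves out between-site variation in change over time, so its 80% holds only if sites in an arm follow nearly the same trend

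*Combined protocol and SAP*

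**What the plan says.** Section 4.1 sets the unit of randomisation: "We will use cluster randomization, with each recruitment site being randomized to one arm of the study". Section 6.3 gives 12 sites in matched pairs, hence six per arm.

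For days of alcohol use, Section 9.2 names its method as "Mixed Models Tests for the Slope Difference in a 3-Level Hierarchical Design with Fixed Slopes (Level-3 Randomization"). The only correlation and the test level appear in the phrase "with subject $icc=0.30$ and $alpha=0.01". The scenarios examined were "for a standardized mean difference (SMD) of 0.50 to 0.70, with cluster sizes of 10, 20. and 30". The claim made for index participants is "we will have at least 80% power to detect a $SMD=0.70". The matching SMDs are 0.50 for network members and 0.41 for everyone combined; the last lies below the range said to have been examined. The number of visits is not stated, and no site-level quantity is given for this outcome.

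The paragraph before, on the binary outcomes, does carry a site-level term: "with an intracluster correlation of 0.05 and alpha=.01".

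Sections 9.4.1 and 9.4.2 plan repeated-measures mixed models with random intercepts for subject and recruitment site. They specify no site-by-time term.

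**The concern.** A fixed-slopes calculation treats every site in an arm as having the same trend. Extra men at the same 12 sites then count as fully independent information about change. The stated SMDs behave that way: SMD × √n is 2.21, 2.24 and 2.25 for 10, 20 and 30 men per site, so the detectable effect falls almost exactly as 1/√n.

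When whole sites are randomised, anything that makes sites drift differently (a work brigade moving on, a local change in drinking, a stronger or weaker training group) adds error that more men per site cannot average away. The optimism is therefore greatest for the complete sample, where the plan claims its smallest detectable effect.

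Sections 1.1 and 3 list heavy alcohol use among the primary endpoints. If the real power is well under 80%, a null alcohol result would be read as stronger evidence of no effect than it is.

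**Working it through.** **Inputs.** From the documents: C = 6 sites per arm (6.3); n = 10, 20, 30 men per site, subject ICC ρ = 0.30 and alpha 0.01 (9.2). Two-sided testing is taken from "exact p-values for 2-tailed tests" in 9.4.1. The cluster sizes are already net of the attrition in 9.2: 70 × 0.90/6 = 10.5, 140 × 0.85/6 = 19.8, and 30.3 together. Assumed: M equally spaced visits, total variance 1, and SMD = slope difference × (M − 1).

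**Step 1: reproduce the plan.** With V_T = (M² − 1)/12,

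Var(slope difference) = 2(1 − ρ)/(C·n·M·V_T)

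Power = Φ[SMD/((M − 1)·SE) − 2.576]; detectable SMD at 80% = (2.576 + 0.842)·(M − 1)·SE.

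For M = 4, V_T = 1.25. With n = 10, SE = √(1.4/300) = 0.0683. Then 0.70/(3 × 0.0683) = 3.416, and Φ(0.840) = 79.9%.

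| | n = 10 | n = 20 | n = 30 |
|---|---|---|---|
| Stated SMD | 0.70 | 0.50 | 0.41 |
| Detectable SMD, M = 4 | 0.700 | 0.495 | 0.404 |
| Power at stated SMD, M = 4 | 79.9% | 80.9% | 81.3% |
| Power at stated SMD, M = 5 | 85.2% | 86.1% | 86.4% |

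There is no computing error. Four visits match closely, and five also satisfy the stated minimum.

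**Step 2: add a stable site effect.** A generalised least squares calculation with site-intercept variance 0.05, subject-intercept variance 0.25 and residual 0.70 again gives 79.9%, 80.9% and 81.3%. The intercept cancels.

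**Step 3: let sites differ in change.** Give each site-visit its own deviation with variance s, taken out of the 0.70. The numerator 1 − ρ then becomes 0.70 + (n − 1)s:

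Var(slope difference) = 2[0.70 + (n − 1)s]/(C·n·M·V_T)

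The documents supply no s. I assume 0.005 to 0.025, which is 10 to 50% of the 0.05 used for the binary outcomes. Example, n = 30, M = 4, s = 0.025: SE = √(2 × 1.425/900) = 0.0563. Then 0.41/(3 × 0.0563) = 2.43, and Φ(−0.147) = 44.1%.

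| Power at stated SMD | n = 10 | n = 20 | n = 30 |
|---|---|---|---|
| M = 4, s = 0.005 | 76.9% | 74.6% | 71.8% |
| M = 4, s = 0.025 | 65.4% | 53.5% | 44.1% |
| M = 5, s = 0.005 | 82.5% | 80.5% | 77.9% |
| M = 5, s = 0.025 | 71.8% | 59.8% | 50.0% |

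A random site slope gives the same picture. With site variance of baseline-to-end change at 0.005, 0.01, 0.02 and 0.05 and M = 4, power is 78/76/73/62% (index), 77/74/67/50% (network) and 76/71/61/41% (all).

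**Step 4: reference distribution.** Twelve sites in two arms leave 10 df (critical value 3.169 instead of 2.576). With the same noncentralities, four-visit power over s = 0.005 to 0.025 is 57.4 to 46.4%, 55.1 to 36.5% and 52.3 to 29.5%.

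**Step 5: shape of the effect.** Take a step change present at all four follow-ups and absent at baseline (T = 0 to 4). Per unit of step over residual SD, the slope contrast has noncentrality 2/√10 = 0.632. The contrast of follow-up mean against baseline has 1/√(1 + 1/4) = 0.894. The squares are 0.4 and 0.8, so the slope carries half the information.

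**The case against.** The plan names its model openly, and its figures follow from that model. A three-level fixed-slopes model can include a site intercept, so it is not true that sites are ignored altogether; step 2 bears this out. The size of the loss in step 3 rests on a variance the documents do not give. With five visits and the smallest value tried, index and network power stay just above 80%. All of this stands, and it limits the point to an omitted variance component and an unstated sensitivity.

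A reader might go further: take the 0.05 from the binary-outcome paragraph, apply the design effect 1 + (n − 1) × 0.05, and conclude that true power is 73%, 58% and 46%, or that the detectable SMDs should be 0.75, 0.62 and 0.56. The documents do not support that. The 0.05 is an outcome-level correlation for binary measures, not a variance of trends. Those figures come from an unadjusted comparison of means at one time point, which has 89.6%, 90.3% and 90.6% power before any inflation. They therefore replace the test and do not correct the 80%.

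Nor would a baseline-adjusted 12-month contrast necessarily do worse. If site effects are stable, as in the model of 9.4.1 (site 0.05, subject 0.25, residual 0.70, equal baseline means), it detects SMDs of about 0.64, 0.47 and 0.39 with 80% power.

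The status of alcohol is also mixed. Sections 6.1.1 and 8.1 name only syringe sharing and condomless sex as primary, and the hypotheses in 9.1 omit alcohol. Section 4.2 already warns that the control programme covers heavy drinking, which limits what can be detected. That lowers the stakes but leaves the power statement uncorrected.

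**Conclusion.** The point holds as a missing variance component, not as an arithmetic error. The 80% is right for a design in which sites within an arm share nearly the same trend. With four visits there is almost no slack, since the figures sit at 79.9 to 81.3% before any site-by-time variance is added. Under the assumed range, power falls by about 3 to 15 points for index participants and about 10 to 37 points for the complete sample. Five visits soften this without removing it.

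These sizes depend on an inferred visit count, an assumed variance and normal critical values. They should be read as sensitivity results, and no single one of them is the true power. The same gap runs into the analysis: with random intercepts only, standard errors for the time-by-arm effect will be too small if site trends differ.

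**What to change.** In Section 9.2:

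- State the number and spacing of visits used in the alcohol calculation.
- State a site-by-time variance, with its source or a label as an assumption.
- Replace the single 80% claim with power, or detectable SMD, across a labelled range of that variance. Use a reference distribution suited to 12 sites.
- Do the calculation for the test that will be used, and carry the matching site-by-time term into the model in 9.4.

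Consider basing both on a baseline-adjusted follow-up contrast in place of a linear slope. The pilot summary in Section 2.2 appears to place the alcohol reduction (31% to 2.3%) by 6 weeks, which is closer to a step than a line. That timing should be confirmed, because 9.2 dates the pilot's syringe and condom results to six months.

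The cost is rewritten text and less favourable stated power. No extra participants or visits are needed, and Section 9.1 says a formal SAP is still to be prepared.

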9 STATISTICAL CONSIDERATIONS

9.1 STATISTICAL HYPOTHESES

- Primary Endpoints:

We hypothesize that, compared to MWID who receive a health education control intervention, those who receive the MASLIHAT peer education intervention will have reduced frequency of syringe and other injection equipment sharing, and reduced frequency of vaginal and anal intercourse without a condom 12 months following the intervention. Alternatively, our null hypothesis is that there will be no difference in the effects of MASLIHAT and the health education control intervention on injection and sexual risk behavior of intervention participants 12 months following the intervention.

We hypothesize that, compared to IDU network members of MWID who receive a health education control intervention, IDU network members of MWID who receive the MASLIHAT peer education intervention will have reduced frequency of syringe and other injection equipment sharing, and reduced frequency of vaginal and anal intercourse without a condom 12 months following the intervention. Alternatively, our null hypothesis is that there will be no difference in the effects of MASLIHAT and the health education control intervention on injection and sexual risk behavior of IDU network members 12 months following the intervention.

- Secondary Endpoint(s):

We hypothesize that, compared to MWID who receive a health education control intervention, those who receive the MASLIHAT peer education intervention will have lower incidence of HIV infection and lower incidence of hepatitis C infection 12 months following the intervention. Alternatively, our null hypothesis is that there will be no difference in the effects of MASLIHAT and the health education control intervention on the incidence of HIV or HCV among intervention participants 12 months following the intervention.

We hypothesize that, compared to IDU network members of MWID who receive a health education control intervention, IDU network members of MWID who receive the MASLIHAT peer education intervention will have lower incidence of HIV infection and lower incidence of hepatitis C infection 12

months following the intervention. Alternatively, our null hypothesis is that there will be no difference in the effects of MASLIHAT and the health education control intervention on the incidence of HIV or HCV among IDU network members 12 months following the intervention.

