For HIV and hepatitis C virus (HCV) outcomes, we computed detectable effects for a one-sided Test for the Difference between Two Poisson Rates in a Cluster-Randomized Design, given our sample with $k=30$ subjects per cluster, coefficient of variation (CV) = 0.50 for the control group and CV=1 for the intervention group, $alpha=0.05$, and $power=0.80$. Assuming a base rate HIV incidence of 10% for the control group, we will have at least 80% power to detect an event rate ratio of 0.11, corresponding to an incidence rate of 1% in the treatment group. For HCV, we must assume that a fair number of the sample will be infected as baseline and therefore excluded from the analysis. Assuming 15 subjects per cluster and HCV base rate incidence of 40%, we will have at least 80% power to detect an event rate ratio of 0.21, corresponding to an incidence rate of 8.6% in the treatment group.

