9.4.3 ANALYSIS OF THE SECONDARY ENDPOINT(S)

Secondary outcomes are HIV and HCV incidence over 12 months. Participants who are HIV antibody positive at baseline will be excluded from the analysis. Participants who are HCV RNA positive at baseline and at 6-months (i.e. chronic infection) will be excluded from the analysis. HCV infection will be operationalized as a positive antibody test following a negative antibody test, or for persons who are AB+ at baseline, a positive HCV RNA test following a negative HCV RNA test. We will conduct a missing data analysis to check for differences between participants with and without test results. If more than 5% of the data are missing we will employ full-information maximum likelihood methods using Mplus.

We will compare incidence rates of HIV and HCV infection between the two intervention conditions among intervention participants, and among network members, with GEE modified Poisson regression to estimate relative risks, adjusted for clustering by recruitment site.⁷⁵ We will estimate the effect of intervention condition, adjusting for covariates including age, education, duration of injection, and length of time in Russia if they are related to the outcome at baseline or if they vary significantly across conditions. The results will be reported as relative risk ratios with 95% confidence intervals, and exact p-values.

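### The 80% power stated for HIV and HCV is for a one-sided test on the pooled sample, but the plan tests index men and network members separately, and neither comparison has that power

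*Combined protocol and SAP*

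**What the plan says.** Section 9.2 bases the HIV and HCV calculation on a one-sided test: "we computed detectable effects for a one-sided Test for the Difference between Two Poisson Rates in a Cluster-Randomized Design". The inputs are 30 men per cluster, a between-cluster coefficient of variation (CV) of 0.50 in control and 1 in MASLIHAT, alpha 0.05 and power 0.80. For HIV, with 10% control incidence, it concludes "we will have at least 80% power to detect an event rate ratio of 0.11" (about 1% incidence under MASLIHAT). For HCV, with 15 men per cluster and 40% control incidence, it concludes "we will have at least 80% power to detect an event rate ratio of 0.21" (8.6%).

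Earlier in 9.2, for the behavioural outcomes, the cluster sizes are defined: "10, 20 or 30 subjects per cluster, representing intervention participants, network members, and the complete sample". So 30 is index men and network members together.

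Section 9.1 states one HIV/HCV hypothesis for index men and a separate one for network members. The null for index men is "no difference in the effects of MASLIHAT and the health education control intervention on the incidence of HIV or HCV among intervention participants". Section 9.4.3 compares incidence "between the two intervention conditions among intervention participants, and among network members". On reporting it says "The results will be reported as relative risk ratios with 95% confidence intervals, and exact p-values", without stating sidedness. It also says "Participants who are HIV antibody positive at baseline will be excluded from the analysis".

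Section 3 and the synopsis set the secondary endpoint as a 50% reduction in 12-month HIV and HCV incidence.

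**The concern.** The power statement describes an analysis that the plan does not contain. Splitting the sample by participant type leaves a third (10 of 30) or two thirds (20 of 30) of the men in each comparison, and no HIV/HCV power is given for either group. Elsewhere 9.2 does work by group: its alcohol figures are given separately for index men, network members and the full sample.

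Three related gaps sit in the same paragraph. Sidedness is not carried through to 9.4.3. The HIV calculation counts every retained man as at risk, although baseline positives will be dropped; 9.2 makes that allowance only for HCV. And the effects described as detectable (reductions of 89% and 79%) are far larger than the 50% the endpoint names.

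If HIV or HCV shows no difference in either group, a reader who trusts 9.2 would treat it as a negative result from a test with 80% power. It would not be one.

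**Working it through.** **Inputs.** 12 sites, one of each matched pair to each arm, so c = 6 per arm (6.3). Control rate l0 = 0.10 for HIV and 0.40 for HCV; MASLIHAT rate l1 = 0.011 (ratio 0.11) and 0.086; CV0 = 0.5, CV1 = 1; alpha 0.05 (all 9.2). Each man is taken to contribute one year.

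**Formula.** The standard sample-size formula for two rates in an unmatched cluster trial, with y men per site:

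c = 1 + (z_a + z_b)² × V / (l0 − l1)², where V = (l0 + l1)/y + CV0²·l0² + CV1²·l1²

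Hence power = Φ[(l0 − l1) × √((c − 1)/V) − z_a], with z_a = 1.645 one-sided or 1.960 two-sided.

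**Step 1: reproduce the plan's figures.**
- HIV, y = 30: V = 0.111/30 + 0.25 × 0.01 + 0.011² = 0.00370 + 0.00250 + 0.00012 = 0.00632. Then 0.089 × √(5/0.00632) = 2.503, and Φ(2.503 − 1.645) = 80.5%.
- HCV, y = 15: V = 0.486/15 + 0.25 × 0.16 + 0.086² = 0.0324 + 0.0400 + 0.0074 = 0.0798. Then 0.314 × √(5/0.0798) = 2.486, and Φ(2.486 − 1.645) = 80.0%.

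Both match 9.2. Two-sided, the same inputs give 71% and 70%, so the stated figures rest on the one-sided test and the pooled sample.

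**Step 2: change only y to the planned groups.** For HIV in index men, y = 10 gives V = 0.01110 + 0.00250 + 0.00012 = 0.01372. Then 0.089 × √(5/0.01372) = 1.699, and Φ(1.699 − 1.645) = 52%. The rest follow the same way. The HCV split of 15 into 5 index and 10 network is an assumption.

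| Comparison | y | One-sided | Two-sided |
|---|---|---|---|
| HIV pooled (not planned) | 30 | 80.5% | 71% |
| HIV network | 20 | 71% | 60% |
| HIV index | 10 | 52% | 40% |
| HCV pooled (not planned) | 15 | 80.0% | 70% |
| HCV network | 10 | 73% | 62% |
| HCV index | 5 | 58% | 45% |

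For HCV splits from 4/11 to 6/9, one-sided power is 53–62% in index men and 75–71% in network members. Even 14 of the 15 in one group gives only 79%. For HIV in index men, a zero rate under MASLIHAT gives only 64% one-sided, so no effect is detectable at 80%.

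**Step 3: baseline HIV exclusions.** Retained men per site are 140 × 0.90/12 = 10.5 index plus 280 × 0.85/12 = 19.8 network, 30.3 in all. So y = 30 leaves no room for exclusions. Section 2.2 gives HIV prevalence among people who inject drugs of 13.5% (Tajikistan) and 25.6% (Russia); applying that range to this sample is an assumption. Multiplying y by 0.865 and 0.744 gives:

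| HIV, after exclusions | One-sided | Two-sided |
|---|---|---|
| Pooled | 77–74% | 67–63% |
| Network | 67–63% | 55–51% |
| Index | 48–44% | 36–32% |

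**Step 4: the 50% target** (HIV 10% to 5%, HCV 40% to 20%). HIV: pooled 30% one-sided and 20% two-sided, network 26% and 17%, index 20% and 12%. HCV pooled: 36% and 25%.

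**The case against.** Section 9.2 contains no slip of arithmetic: both figures are right for the test and sample it openly names. That stands; the fault is that the planned analysis differs.

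On sidedness, the alternatives in 9.1 are directional, which suits a one-sided test. Section 9.4.1 mentions two-tailed tests, but directly after the logistic regression comparison of follow-up, so it does not clearly govern 9.4.3. A formal SAP is promised before the first interim analysis and could settle this. Sidedness is therefore unresolved rather than contradicted, and the shortfall appears under either reading.

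The strongest point is that the plan gives one pair of CVs for the pooled site, so the group figures need CVs it does not supply. Varying the control CV from 0.25 to 0.75, one-sided:
- HIV: index 57–46%, network 81–59%.
- HCV (5/10 split): index 67–48%, network 86–58%.

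Network members can therefore pass 80%, but only one-sided and with a control CV below the plan's 0.5 (about 0.38 for HCV, about 0.25 for HIV). Index men never do.

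The 15 susceptible men per site for HCV may also be low. At the bottom of the 23–67% HCV prevalence range in section 2.2, 20 × 0.77 = 15.4 network members per site would be susceptible, giving 80.3% one-sided and about 70% two-sided. That replaces the plan's own input with its most favourable alternative.

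Dropping the one-cluster correction (c in place of c − 1) gives, one-sided, HIV network 78% and index 59%, and HCV network 79.9% and index 65%. But it puts pooled HIV at 86%, so it does not reproduce 9.2.

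Finally, these are secondary endpoints, and 9.4.3 already reports relative risks with intervals. That limits the consequence but does not supply the power claimed.

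**Conclusion.** The concern holds. The 80% power stated for HIV and HCV belongs to a pooled one-sided comparison that 9.1 and 9.4.3 do not plan. With the plan's inputs, the comparisons it does plan have 52% to 73% power one-sided and 40% to 62% two-sided, before any baseline HIV exclusions. The group figures assume that the plan's CVs apply within each group and, for HCV, a 5/10 split of the 15 susceptible men. The shortfall in index men survives every variation tried. In network members it could be closed only one-sided, and only with a smaller control CV or more susceptible men than the plan assumes. The 50% reduction named as the endpoint has low power on any reading, at most 36% pooled. The point should be fixed, but it does not touch the primary behavioural outcomes.

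**What to change.** - In 9.4.3, state whether the HIV and HCV tests are one- or two-sided, and make 9.2 match.
- In 9.2, give HIV and HCV power for index men and network members separately, stating the CVs and the HCV split assumed. For HIV, show it over a range of baseline prevalence.
- Report the power for the 50% reduction, and present the HIV and HCV results chiefly as incidence ratios with intervals.

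Alternatively, name the pooled index-plus-network comparison as the main HIV/HCV analysis, amend 9.1, 9.4.3 and the secondary objective to agree, and keep the two groups as descriptive. That choice is a design preference. It would still need sidedness stated, the HIV exclusions allowed for and the power for the 50% target given.

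The cost is protocol and SAP wording and less favourable stated power. No extra participants are needed.
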